#### 4.2.2 Secondary Endpoints

1. To compare the two atrial ATP Programming arms in terms of clinical endpoints reported below:
  - all-cause death (at the end of 24 months), measured as time to event;
  - cardiovascular hospitalization (HF, AF or other), measured as time to first event and annual rate;
  - Annual rate for all-cause hospitalization;

- AT/AF burden metrics, measured in terms of time to first event (daily burden  $\geq 1$  day,  $\geq 2$  days,  $\geq 30$  days) or the ratio between time in AT/AF and the observation period;
  - number of successful and unsuccessful treated AT/AF episodes out of detected episodes;
  - number of delivered therapies per episode;
  - number of ATP sequences;
  - stroke, TIA or other thromboembolic events;
  - LA diameter (where available);
  - percentage of patients treated by anticoagulation therapy according management guideline;
  - electrical or pharmacological cardioversions, measured as time to first event and annual rate;
  - biventricular pacing percentage (in CRT-P /CRT-D patients).
2. Composite endpoint made of death, cardiovascular hospitalizations, stroke, TIA or other thromboembolic events;
  3. To evaluate the incidence of persistent AF in patients with sick sinus syndrome compared to the one found in the Minerva trial, and characterize the difference between the European and Indian populations;
  4. To evaluate the efficacy of atrial ATP therapies as a function of the device type (IPG, ICD, CRT-D, CRT-P), and population characteristics (baseline characteristics, implant indications).

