### 7.1.3 Analysis Sets

The following analysis sets were defined in the CIP:

- The Per Protocol Analysis Set (PP) includes all patients actively enrolled in the study, who signed Informed Consent Form (ICF), fulfilled the inclusion/exclusion criteria and that have one day in Sinus Rhythm at the time of enrollment or after the enrollment.
- The Intention-to-Treat Set (ITT) includes all patients actively enrolled in the study, who signed ICF, and fulfilled the inclusion/exclusion criteria.

Since the study was terminated early with low number of patients enrolled, no significant differences in terms of sample size between the PP and ITT population sets are expected. Moreover, the device data interrogation compliance, due to the COVID-19 pandemic, was far from what expected in the investigation plan. For these reasons the Full Analysis Set (FAS) including all patients randomized into the study and fulfilling the inclusion/exclusion criteria will be used throughout the analysis.

The primary endpoint and the secondary endpoints will be analyzed in the FAS population with descriptive statistics without testing formal hypotheses. For the same reason no analyses on subsets of the FAS as outlined in the study protocol will be performed. In addition, individual subject listings could be generated, if needed.

The randomization arm will be used throughout the analysis.

Information about, patients assigned to the different treatment arm then the arm to which the patient was randomized (i.e. wrong device programming in terms rATP feature), will be reported in the protocol deviation table or listing if needed.

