### **7.2.2 Derived Variables**

Variables to evaluate the primary endpoint, as well as daily AF burden metrics, number of successful and unsuccessful treated AT/AF episodes out of detected episodes, number of delivered therapies per episode, and number of ATP sequences will be derived from the device datasets and will be described in detail in the SPR (ref).

The exposure time (months) for the time to first persistent AF will be computed from the date of randomization to the date of the last device save to disc for patients without persistent AF recurrence or to the date of first recurrence of persistent AF recurrence otherwise  $[(\text{data end} - \text{data in})/30.4]$ .

Variables to evaluate secondary endpoints as all-cause death, cardiovascular hospitalization (HF, AF or other), stroke, TIA or other thromboembolic events and annual rate for all-cause hospitalization will be derived from the adverse event dataset and will be described in detail in the SPR (ref).

The exposure time (months) for the secondary endpoints will be computed from the date of randomization to the date of the notice (follow-up visit or adverse event) for patients without events or to the date of the specific event otherwise  $[(\text{data end} - \text{data in})/30.4]$ .

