## 7.4 Handling of Missing, Unused, and Spurious Data and Dropouts

Since the impact of missing data is expected to be small, and only descriptive statistics will be applied no multiple imputation method for missing data is planned. For subjects who are lost to follow-up, the time to event will be censored at the last available contact date.

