## 7.9 Evaluation of Objectives

Endpoints defined in the section 4.2 will be used to evaluate objectives.

A device data quality analysis will be performed before the derivation of the analysis variables. Endpoints based on device data could be biased by the not compliance of the device data interrogation process compared to the clinical investigation plan.

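### SAP 7.2.2 ties exposure to device data for the primary endpoint only, so burden follow-up can run past the last device read and ATP sequences have no time base

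*SAP*

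**What the plan says.** SAP 4.2.2 lists AT/AF burden as a secondary endpoint, measured as time to first event at thresholds of 1, 2 and 30 days, "or the ratio between time in AT/AF and the observation period". No section defines the observation period. The same list gives "number of ATP sequences" with no unit of time. By contrast, "number of successful and unsuccessful treated AT/AF episodes out of detected episodes" and therapies per episode carry their own denominators.

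SAP 7.2.2 sets two exposure clocks. The primary endpoint's is "computed from the date of randomization to the date of the last device save to disc for patients without persistent AF recurrence". For the rest, "The exposure time (months) for the secondary endpoints will be computed from the date of randomization to the date of the notice", which the text explains as a follow-up visit or adverse event. No secondary endpoint is exempted. SAP 7.4 censors patients lost to follow-up at the last contact. SAP 7.2.2 also says that burden and ATP variables come from the device datasets, and leaves the details to the Statistical Programming Requirements (SPR), which is not among the documents.

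On completeness, SAP 7.1.3 reports that "the device data interrogation compliance, due to the COVID-19 pandemic, was far from what expected in the investigation plan". SAP 7.9 warns: "Endpoints based on device data could be biased by the not compliance of the device data interrogation process". SAP 7.4 declines imputation with the words "Since the impact of missing data is expected to be small", adding that the analysis is only descriptive.

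**The concern.** A device-derived event or AF hour can be recorded only for time that a device read covers. If follow-up for such an endpoint ends at a clinic visit or an adverse event report, any stretch after the last read counts as observed time in which nothing could have been seen. Such contacts are foreseeable: Protocol 9.8 allows adverse events to be reported by telephone, and remote reads exist only for patients on remote monitoring. The SAP evidently recognised the need for a device-based end date, since it gave the primary endpoint one.

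Burden and ATP sequences are the endpoints that show what the reduced programming did. SAP 5 states that the interventional setting is meant to halve the number of ATP sequences. A burden estimate pulled toward zero, or a raw count that mixes therapy rate with length of record, would blur that description. Uneven device coverage between arms could create or mask a difference.

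**Working it through.** The plan states no figure for these endpoints, so there is none to reproduce. The planned 758 patients concern the primary endpoint and have no bearing here. The check has two parts.

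**1. Source of the data against the end of the clock (SAP 4.2.2, 7.2.2, 7.4)**

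| Endpoint | Source | Time base in the SAP | Match? |
|---|---|---|---|
| Persistent AF (primary) | Device | To last save-to-disc | Yes, at its end |
| Death, hospitalisation, stroke/TIA | Adverse event data | To visit or adverse event | Yes |
| Burden, time to first event | Device | To visit or adverse event, read literally | No |
| Burden ratio | Device | Undefined | No, if the same clock is used |
| ATP sequences | Device | None | No time base |
| Treated episodes; therapies per episode | Device | Detected episodes; episode | Not affected in this way |

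For a patient without a burden event, let D be the date of the last device read and V the later date of the last visit or adverse event. The literal rule keeps the patient at risk for V − D further days in which no burden event can be recorded. Protocol 13.2.9 has the same feature: its end dates include the last follow-up visit and study exit as well as the last transmission.

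**2. Arithmetic if uncovered time stays in the denominator**

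Let c be covered days divided by days in the denominator. Then reported burden = true burden × c. The documents give no value for c, so it is assumed over 50% to 100%. With a true burden of 10%:

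- c = 90%: 0.10 × 0.90 = 9.0%
- c = 75%: 0.10 × 0.75 = 7.5%
- c = 60%: 0.10 × 0.60 = 6.0%
- c = 50%: 0.10 × 0.50 = 5.0%

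Equal coverage shrinks the absolute difference but keeps the ratio. At 75%, true burdens of 10% and 20% read 7.5% and 15%: the gap falls from 10 to 7.5 points, and the ratio stays 2.

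Unequal coverage creates a difference. With a true 10% in both arms and coverage of 90% and 60%, the arms read 9% and 6%, a false ratio of 0.06/0.09 = 0.67.

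For raw ATP counts, take the intended 50% reduction (SAP 5) as true. Reported reduction = 1 − 0.5 × (interventional coverage / control coverage).

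- Interventional 60%, control 90%: 1 − 0.5 × 0.60/0.90 = 67%
- Interventional 90%, control 60%: 1 − 0.5 × 0.90/0.60 = 25%

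Even with full coverage, a bare count grows with time. At the same rate, 24 months of record yields 24/6 = 4 times the count of 6 months (lengths chosen for illustration).

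With covered days as the denominator, c cancels. Burden returns to 10% and the reduction to 50%, provided uncovered days resemble covered ones.

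**The case against.** The best defence is that the SAP does not finish the specification. Burden and ATP derivations are deferred to the SPR, which may define the denominator properly. The visit-or-adverse-event clock directly follows the paragraph on adverse-event-derived endpoints, and its wording about the date of the specific event does not suit a ratio. The primary endpoint's clock suggests that the authors understood device data. All this makes the burden denominator ambiguous rather than wrong. It does not clear the burden time-to-event endpoints: the clock is worded for the secondary endpoints at large, and an SPR that used covered days for them would contradict it.

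Second, a missed interrogation is not necessarily a gap. Reads retrieve stored episodes and trends (Protocol 9.1.2 and 9.6), and SAP 5 schedules a final visit for ongoing subjects in June to July 2021. This stands. The clear exposure is time after the last read. Gaps between reads depend on storage capacity, which is not given.

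Third, SAP 7.9 plans a device data quality analysis and SAP 7.12 defers the decision on endpoint evaluation until data quality is known. These help, but neither sets a coverage rule, and the denominator could then be chosen after seeing the data. SAP 7.9.2 offers annual rates for appropriate endpoints without naming ATP sequences or their exposure.

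Fourth, nothing shows that coverage differs by arm. The shortfall is put down to the pandemic, and patients are blinded. Investigators do know the assignment (Protocol 10.3), so a difference cannot be excluded, but it remains an assumption.

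**Conclusion.** The point holds in limited form. SAP 7.2.2 states a clock that, taken literally, gives device-derived burden time-to-event endpoints follow-up that no device record supports. The burden ratio has an undefined denominator that the same clock might fill. ATP sequences lack a time base although follow-up is unequal. The small-impact statement in 7.4 conflicts with 7.1.3 and 7.9 as far as device data are concerned.

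A reader might infer that the plan counts every period without device data as AF-free, or that all ATP endpoints are diluted. The documents do not support either. No section says the former, and treated episodes and therapies per episode have device-based denominators.

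The size is unknown. The figures above rest on assumed coverage and on uncovered time staying in the denominator. The analysis covers 75 patients (37 and 38 per arm) with no tests or hazard ratios, so the consequence is misleading arm summaries and not a wrong test decision. The change is still worth making, because it is cheap and the SAP itself reports the compliance problem.

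**What to change.** In SAP 7.2.2:

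- Limit the visit-or-adverse-event clock to the clinical secondary endpoints.
- For device-derived secondary endpoints, end exposure at the last save-to-disc or last retrieved transmission.
- Define the burden observation period as post-randomisation days covered by retrieved device data.
- Report ATP sequences per covered patient-year.

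Also report covered days over follow-up days by arm, and remove or qualify the statement in 7.4 that missing data should have little impact, as it applies to device data. The SPR should carry the same definitions.

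I would not censor at the first gap in the record. That choice is debatable and would discard valid later data in a small study.

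The cost is SAP wording and one derived variable, with no new kind of data to collect. The downside is fewer patient-days, with some patients contributing short periods.

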## 5. Investigation Plan

---

MANDATE AF is a prospective, multi-center, randomized, single-blind study.

The study analyses patients implanted with a Medtronic cardiac implantable device with an atrial lead and equipped with atrial ATP therapies. The patients should have been implanted for no more than 18 months prior to enrollment.

The patients are randomized into two groups:

- a control arm including patients with the same atrial ATP therapies programming setting adopted in the Minerva trial;
- an interventional arm including patients with a conservative atrial ATP therapies programming setting that is intended to reduce number of ATP sequences by 50% compared with the control arm.

Study required adverse events will be collected prospectively for at least 24 months after enrollment. Physicians will be recommended to schedule in clinic follow-up visits every 6 months and remote follow-up visits every 3 months in between.

Every patient will be followed for at least 24 months, until the last patient enrolled exits the study.

[figure not shown]

Figure 1- Study Flowchart

However, the study was terminated earlier in August 2021 due to problems in enrollment, changes in product portfolio, very minimal Reactive ATP enabled devices available, and change in the local evidence strategy with a sample size of approximately 75 patients (10% of estimated sample size) and with a final follow-up visit for ongoing subjects scheduled between June and July 2021.

## 6. Determination of Sample Size

---

The original study design aimed to recruit 758 (379 per arm) patients. The power calculations assumed a noninferiority margin of 7.5%. The survival was planned to be assessed at 24 month and the assumed survival probabilities were 85% for control arm and 77.5% or more for the experimental arm. The study had following assumptions:

- The accrual time is expected to be approximately 18 months for both arms.
- The total study exposure is expected to be at maximum 42 months for both arms.
- The follow-up time 24 months.
- Proportion of subjects lost to follow-up in the control and experimental groups 15%
- The sample size should be enough to produce an 80% chance (power) of a significant result at a one-sided 0.025 significance level.
- The non-inferiority margin that characterizes the largest absolute difference considered to be dismissible at 24 months is defined as 7.5%.
- History of AF is a stratification factor.

The calculations were performed by statistician using SAS software version 9.4 (SAS Institute Inc., Cary, NC, USA).

The study was terminated prematurely when 79 patients were screened and 75 (37 and 38 in the interventional and in the control arm, respectively) enrolled fulfilling the inclusion/exclusion criteria.

## 7. Statistical Methods

---

### 7.1 Study Subjects

#### 7.1.1 Disposition of Subjects

The number of patients assessed for eligibility, enrolled, randomized, number of patients with follow-up visits completed and the number of patients with device data interrogation available will be summarized by table and by flow-chart.

The reason for study exit will be presented in table.

### 7.1.2 Clinical Investigation Plan (CIP) Deviations

Protocol deviations should be reviewed prior to study reporting by the study team. The counts and percentages protocol deviations will be presented in descriptive tables, overall and by follow-up visit.

### 7.1.3 Analysis Sets

The following analysis sets were defined in the CIP:

- The Per Protocol Analysis Set (PP) includes all patients actively enrolled in the study, who signed Informed Consent Form (ICF), fulfilled the inclusion/exclusion criteria and that have one day in Sinus Rhythm at the time of enrollment or after the enrollment.
- The Intention-to-Treat Set (ITT) includes all patients actively enrolled in the study, who signed ICF, and fulfilled the inclusion/exclusion criteria.

Since the study was terminated early with low number of patients enrolled, no significant differences in terms of sample size between the PP and ITT population sets are expected. Moreover, the device data interrogation compliance, due to the COVID-19 pandemic, was far from what expected in the investigation plan. For these reasons the Full Analysis Set (FAS) including all patients randomized into the study and fulfilling the inclusion/exclusion criteria will be used throughout the analysis.

The primary endpoint and the secondary endpoints will be analyzed in the FAS population with descriptive statistics without testing formal hypotheses. For the same reason no analyses on subsets of the FAS as outlined in the study protocol will be performed. In addition, individual subject listings could be generated, if needed.

The randomization arm will be used throughout the analysis.

Information about, patients assigned to the different treatment arm then the arm to which the patient was randomized (i.e. wrong device programming in terms rATP feature), will be reported in the protocol deviation table or listing if needed.

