8.2. Subject Enrollment

The point of enrollment is defined as the time at which the inclusion and exclusion criteria have been checked and fulfilled and at which a subject and the investigator have signed and dated the PIC form. At that point, the patient can be enrolled on the study. A study patient ID number will be assigned, and the patient must be followed until study closure or study exit, whichever occurs first. The investigator will record on the medical file of the patient that he/she participates in the study. Up to 758 patients will be enrolled with about 379 patients randomized into each arm, this study does not set a minimum number per site as the enrollment will be competitive.

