9.1.1. Baseline visit

Subjects may be enrolled into the study only after a minimum of 6 weeks from implant, or after leads stabilization (based on physician's discretion), to be sure about leads fixation.

During the baseline visit, the subject will be randomly assigned to one of the two study groups: intervention arm or control arm. If the atrial ATP therapies are already ON at the time of the randomization, the setting will be changed according to the assigned arm.

After enrolling the patient, the following data will be collected:

- **Demographics**, such as age and gender;
- **Medical History**, such as etiology, history of cardiovascular and arrhythmia events and surgical intervention as well as history of co-morbidities will be documented after enrolling a patient;
- Symptoms;
- **Device Data**, comprehensive of:
 - arrhythmic episodes stored in the device memory;
 - clinically significant changes in Cardiac Compass parameters (as per physician's opinion);
 - electrical parameters (leads impedance, sensing, threshold);
 - AT/AF therapies programming setting;

- ECG data: At the time of baseline (where available) from the patients' medical records (if done on the same day or ± 1 month from the date of the visit)
- **Echocardiographic (ECHO) data** obtained by performing an ECHO test (where available):
 - The test can be done on the same day of the baseline assessment, if recommended;
 - retrieving a previous ECHO exam not older than 1 month (± 2 weeks) from the baseline assessment;
 - scheduling an ECHO test in 1 month (± 2 weeks) from the baseline assessment;

- Medications.

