9.9. Deviation Handling

A study deviation is an event where the investigator or site personnel did not conduct the clinical study according to the Clinical Investigational Plan or Clinical Investigation Agreement. The investigator is not allowed to deviate from the above-mentioned documents except with prior approval or under emergency circumstances to protect the rights, safety and wellbeing of the subject. All deviations shall be documented and explained, regardless the reason for the deviation.

Deviations will be collected on electronic Case Report Forms (eCRF). Investigators must report study deviations to Sponsor in a timely manner. Study deviations may include but are not limited to:

- missing follow-up visits;
- failure to obtain Informed consent Form prior to participation in the study;
- incorrect version of consent form provided to subject;
- not performed Protocol Required Data Collection/Testing;
- subject did not meet enrollment criteria;
- incorrectly performed testing;
- source data permanently missing.

Sponsor will review deviations as they are received. Corrective and preventative actions may be discussed with the site as needed.

The following will not be considered study deviations:

- incomplete data due to subject exit or withdrawal;
- no data collected from study components that are optional.

Medtronic will assess the significance of all deviations and evaluate the need to amend the CIP or to early terminate the investigation, in accordance with Medtronic standard operating procedures (SOPs).

Substantial and non-substantial amendments to the protocol will be notified to the IEC for notification and/or approval if required according to site requirements.

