10.3. Risk-Benefit Rationale

The conclusion of the risk assessment is that the benefits outweigh the risk for the patient; therefore, the investigation is justified. It is possible in any clinical study that harmful things can happen which is not known at this time.

The Investigator will continue monitoring, assessing and documenting any additional risk identified during the conduct of the study and the risk-to-benefit analysis updated accordingly.

To minimize or avoid bias the MANDATE study has been designed as a randomized, single-blind trial, where the patient

Each patient's assignment onto the respective arms on the study will be concealed in the study database (Oracle Clinical) and not revealed until all baseline data has been collected and the patient is considered eligible for randomization after having met the eligibility criteria. Investigators accessed patient

Medtronic Controlled Information

randomization through the study database and will further assign the patients who remained blind as for treatment arm onto the respective randomization arms.

11. Adverse Events

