13.2.2. Analysis sets

The following population sets will be considered:

- The Per Protocol Analysis Set (PP) includes all patients actively enrolled in the study, who signed Informed Consent Form (ICF), fulfilled the inclusion/exclusion criteria and that have one day in Sinus Rhythm at the time of enrollment or after the enrollment.
- The Intention-to-Treat Set (ITT) includes all patients actively enrolled in the study, who signed ICF, and fulfilled the inclusion/exclusion criteria.

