13.2.10. Safety

Adverse events in the ITT will be presented in summary tables and supporting data listings.

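### As written, the Full Analysis Set would drop any randomised patient later judged ineligible, from the safety tables as well as the efficacy summaries

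*SAP*

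**What the plan says.** **Efficacy set.** SAP section 7.1.3 replaces the protocol's two sets with one FAS, which "including all patients randomized into the study and fulfilling the inclusion/exclusion criteria will be used throughout the analysis". Patients are analysed in the arm to which they were randomised. Protocol section 13.2.2 had already placed the eligibility condition on the set it calls ITT, which "includes all patients actively enrolled in the study, who signed ICF, and fulfilled the inclusion/exclusion criteria"; that definition does not mention randomisation.

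**Safety set.** Protocol section 13.2.10: "Adverse events in the ITT will be presented in summary tables and supporting data listings". SAP section 7.10 describes the adverse event tables but names no population for them, so the FAS applies by default.

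**Eligibility before randomisation.** Protocol section 8.2 defines enrolment as "the time at which the inclusion and exclusion criteria have been checked and fulfilled", together with signed consent. Protocol section 10.3 says the assignment is "not revealed until all baseline data has been collected and the patient is considered eligible for randomization".

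**Ineligible enrolment is foreseen.** Protocol section 9.9 lists "subject did not meet enrollment criteria" among the deviations. Protocol section 9.10 gives a breach of the randomisation criteria as an example of a reason for withdrawal.

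**Counts.** SAP section 6 reports 79 screened and 75 enrolled who met the criteria, 37 interventional and 38 control.

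**The concern.** An intention-to-treat type of set should be fixed by randomisation alone. Here a second condition, eligibility, can be decided or revised after the device has been reprogrammed to the assigned arm.

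The study is single-blind. The patient is blinded, but the investigator obtains the assignment and therefore knows it. SAP section 7.1.2 has the study team review deviations before reporting and does not ask that this be done blind to arm. The SAP is dated 27 August 2021, after the final visits of June and July 2021 and days before the scheduled database lock. One exclusion criterion, persistent AF at baseline, is read from the same device diagnostics that supply the primary endpoint. A later re-reading of baseline device data could therefore bear on the patients most prone to events.

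The safety side matters most. A randomised patient has received the assigned programming. If that patient is later classed as ineligible, any death, serious event or device event would fall outside the summary tables. A trial stopped at about a tenth of its target can still deliver a complete safety count, and this rule puts that at risk.

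**Working it through.** The point rests on a definition, so the first step sets the texts side by side. The arithmetic then bounds its size.

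**1. Who is in which set**

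| Patient | Protocol ITT (13.2.2) | SAP FAS (7.1.3) | Adverse event tables |
|---|---|---|---|
| Randomised, eligible | in | in | in |
| Randomised, later judged ineligible | out | out | out (13.2.10 through ITT; SAP 7.10 through the FAS) |
| Screen failure, never randomised | out | out | out |

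Only the middle row is at issue. The planned disposition flow chart (SAP 7.1.1) and deviation table (SAP 7.1.2) could make such a patient visible. Neither puts the patient back into an estimate or an adverse event count.

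**2. The plan's own counts.** 37 + 38 = 75, as SAP section 6 states. 75/758 = 9.9%, which agrees with the SAP's description of about 10% of target. The planned 758 rests on event rates, margin, error rates and loss to follow-up, and does not change with the definition of the set.

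**3. How many could be affected.** Taking the 75 as final, 79 − 75 = 4 screened patients are unaccounted for. 4/79 = 5.1%. If all 4 had been randomised (an assumption; the SAP does not say), the FAS would cover 75/79 = 94.9% of randomised patients. If none had, it covers 100%.

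**4. Effect of one patient on a crude proportion.** Dropping a patient with an event from x events in n changes the proportion by x/n − (x−1)/(n−1) = (n−x)/[n(n−1)]. This is largest at x = 1, where it equals 1/n: 1/37 = 2.7 points or 1/38 = 2.6 points.

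With more events the shift is smaller. Assume, for illustration, 6/37 = 16.2% in the interventional arm:
- drop one patient with an event: 5/36 = 13.9%, a fall of 2.3 points;
- drop one patient without an event: 6/36 = 16.7%, a rise of 0.5 points;
- add back one patient with an event: 7/38 = 18.4%, a rise of 2.2 points.

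**5. Outer bound.** Under the same assumption, adding all 4 to the interventional arm gives 6/41 = 14.6% if none had an event and 10/41 = 24.4% if all did: shifts of −1.6 and +8.2 points. The upper figure needs all 4 to have been randomised, all to one arm, and all to have had the event. It is a limit, not an expectation. Crude proportions stand in here for Kaplan-Meier estimates.

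**The case against.** The best defence is that the condition may only restate how enrolment works. Criteria are checked before consent is complete, and the arm is withheld until the patient is considered eligible. On that reading the 4 patients are screen failures and the FAS already equals all randomised patients. This is plausible and may be what happened. It does not rescue the wording, because the protocol itself foresees ineligible enrolment, and the rule says what then follows.

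A reader might be tempted by four stronger conclusions. The documents support none of them.

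- **Randomised patients were removed.** No passage shows this. No passage describes a post-randomisation review whose purpose is to remove patients; the deviation review only records and tabulates.
- **The trial is open-label.** It is single-blind. What stands is that investigators know the arm and nothing requires the study team to be blind.
- **A non-inferiority conclusion is at risk.** SAP sections 7.1.3, 7.9.1 and 7.12 exclude formal testing, and 7.9.1 also excludes a hazard ratio. The 7.5-point margin is therefore not a relevant yardstick.
- **Serious events would go unreported.** Protocol section 11.2.1 requires all of them to go to the sponsor and ethics committee, whatever the analysis set. The gap is in the summary tables.

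There is also some slack in the safety reading. SAP section 7.2.1 calls the FAS the main set, SAP section 7.10 is silent on population, and listings are provided if needed. The inference that the tables use the FAS is sound but not explicit, which is a further reason to state the population.

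**Conclusion.** The point holds as a defect in a stated rule. Both definitions would exclude any randomised patient later judged ineligible, and the exclusion would carry into the adverse event tables. The number affected is unknown, from 0 to 4 on the SAP's counts, and zero is quite possible. One patient with an event is worth at most about 2.7 points in one arm. The consequence is incomplete descriptive estimates and safety counts, with possible dependence on arm or outcome. Type I error and non-inferiority are not affected.

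This assumes that the 75 are final and that SAP section 7.10 follows the FAS.

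A separate matter also needs attention. Inclusion criterion 1 (protocol section 8.3) requires at least 6 weeks since implant, while section 9.1.1 allows enrolment "only after a minimum of 6 weeks from implant, or after leads stabilization" at the physician's discretion. These passages must be reconciled. The documents do not say how a patient enrolled under the second clause would be classed, so it cannot be concluded that this wording produced ineligible patients.

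**What to change.** - **SAP 7.1.3:** define the FAS as all randomised patients, analysed in the arm assigned by randomisation. Retain patients found ineligible and list them as deviations with the reason. Any set restricted to eligible patients is then a sensitivity summary.
- **SAP 7.10:** state that the safety tables include all randomised patients.
- **Disposition flow chart (SAP 7.1.1):** say for each of the 4 patients not among the 75 whether they were randomised and, if so, to which arm. If none was, one line saying so closes the question.
- **Protocol 8.3 and 9.1.1:** reconcile the timing of enrolment after implant.

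The analysis changes cost a few sentences and use data already collected. A patient withdrawn early would contribute data up to exit. Because the SAP has superseded the ITT set for this terminated study, amending protocol section 13.2.2 would add little. If the database is already locked, SAP section 7.2.1 allows the change to be made as a deviation, described and justified in the Clinical Study Report.
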